8.5 Day Ranges for Analysis of Time Points

Subjects who do not always adhere strictly to the visit schedule timing in the protocol. Therefore, the designation of visits during the treatment period of the study will be based on the day of evaluation relative to the trial (day of first study medication = study Day 1) rather than the nominal visit recorded in the eCRF. Mutually exclusive relative day windows are defined below to provide derived visits that correspond to the post-baseline time points. If a visit falls outside of the pre-specified visit windows, then the data collected at that visit will not be assigned a derived visit but will remain in the derived data sets. Determination of baseline values is addressed in Section 8.2.

If a subject has more than 1 visit where a measurement is recorded within a window, the measurement closest to the target day will be used. In case of 2 visits being equidistant from the target, the earlier measurement will be used in analyses. For these safety indicators, the least favorable value (toward a positive response) in the window will be used.

Designation of visits for efficacy assessments during the treatment period is tabulated below.

Table 8.5-1: Day Ranges for Efficacy Assessments

Visit	Target Day	Days Range
Baseline/Day 1	1	1
Day 8	8	2-11
Day 15	15	12-22
Day 29	29	23-43 *
Day 57	57	44-71
Day 85	85	72-100

* DLQI is not assessed on Day 8 and Day 16. Days range for DLQI of Day 29 is 2-43.

9 CONTENT OF REPORTS

All analyses described in this SAP will be included in the Clinical Study Report except where otherwise noted. Other analyses may be performed upon the request of the study team. Refer to the Data Presentation Plan for mock-ups of all tables and listings.

█ █
█ █
█ █

11 DOCUMENT HISTORY

Table 10-1: Document History

Version	Author	Summary of Changes
1.0	[name]	Original version
2.0	[name]	
 • Revised the definitions of some endpoints 
 - Changed “after 12 week” to “at Day 85” - Revised wording for secondary endpoints in Section 4.2 • Further clarified the analysis: 
 - Rearranged the analyses Sections - Added how to calculation PASI-75 from the PASI scores - Added sub-sections for subgroup analysis, sensitivity analysis, and per-protocol analysis under section 7.5 - Added “change from baseline” or “percentage change from baseline” for continuous efficacy endpoints and key endpoints (PASI-75, etc.) in the listing - Added a treatment compliance section under section 7.4 - Modified listing for study medication administration - Changed confidence level from 90% to 95% • Fixed several typos in the text • Fixed format for some bullets

APPENDIX 1 RELEVANT PROTOCOL DEVIATIONS

Eligibility Deviations:

- Subjects with a diagnosis of plaque psoriasis for < 6 months
- Body mass index (BMI) not within 18-40 kg/m² or total body weight ≤ 50 kg (110 lb.)
- Subject with psoriatic plaques cover < 10% of body surface area (BSA)
- Subject with PASI score < 12 or sPGA < 3

- Diagnosis of non-plaque psoriasis

Incorrect dosing:

- Subjects who receive treatment different than randomized group
- Subjects taking less than 80% or more than 120% of the planned medication during the entire treatment period
- Randomized subjects who do not take any blinded study medication for \geq two consecutive weeks
- Restricted and Prohibited medications (refer to Protocol Section 3.4.1):
- Subjects receiving prohibited concomitant treatments while on study therapy. The prohibited and/or restricted treatments are described in Table 3.4.1-1 of the study protocol.

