 - d) Any history of known or suspected congenital or acquired immunodeficiency state or condition that would compromise the subject's immune status (e.g., history of splenectomy, primary immunodeficiency, HIV infection, etc.)

6. Medical History and Concurrent Diseases

- a) Any significant acute or chronic medical illness
- b) Any major surgery within 4 weeks of study drug administration
- c) Blood transfusion within 4 weeks of study drug administration

- d) Recent (within 6 months of study drug administration) drug or alcohol abuse as determined by the Investigator
- e) Any major illness/condition or evidence of an unstable clinical condition (e.g., renal, hepatic, hematologic, gastrointestinal, endocrine, pulmonary, immunologic, or local active infection/infectious illness) that, in the Investigator's judgment will substantially increase the risk to the subject if he or she participates in the study
- f) Has unstable cardiovascular disease, defined as a recent clinical deterioration (e.g., unstable angina, rapid atrial fibrillation) in the last 3 months or a cardiac hospitalization within the last 3 months.
- g) Class III or IV congestive heart failure by New York Heart Association Criteria
- h) Has been hospitalized in the past 3 months for asthma, ever required intubation for treatment of asthma, currently require oral corticosteroids for the treatment of asthma, or required more than one short-term (≤ 2 weeks) course of oral corticosteroids for asthma within the previous 6 months
- i) History of cancer (solid organ or hematologic including myelodysplastic syndrome) or lymphoproliferative disease within the previous 5 years (other than resected cutaneous basal cell or squamous cell carcinoma that has been treated with no evidence of recurrence)
- j) Inability to tolerate oral medication
- k) Inability to be venipunctured and/or tolerate venous access
- l) Any other sound medical, psychiatric and/or social reason as determined by the Investigator
- m) History of lack of response to ustekinumab, secukinumab or ixikizumab (any therapeutic agent targeted to IL-12, IL-17 or IL-23) at approved doses after at least 3 months of therapy
- n) Has received ustekinumab, secukinumab or ixikizumab (any therapeutic agent targeted to IL-12, IL-17 or IL-23) within 6 months of first administration of study medication
- o) Has received anti-TNF α inhibitor(s) within 2 months of first administration of study medication

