3.4 Concomitant Treatments

3.4.1 Prohibited and/or Restricted Treatments

Prohibited and/or restricted medications taken prior to study drug administration in the study are described below in [Table 3.4.1-1](#). Medications taken within 4 weeks prior to study drug administration must be recorded on the CRF.

Table 3.4.1-1: Prohibited and or Restricted Treatments

Prohibited Treatments	Washout Period (before randomization)
Ustekinumab, secukinumab or ixikizumab (any therapeutic agent targeted to IL-12, IL-17, or IL-23)	6 months
TNF α inhibitors	2 months
Natalizumab, efalizumab, or agents that modulate B cells or T cells (e.g. alemtuzumab, abatacept, alefacept, visilizumab)	3 months
Rituximab	6 months
Systemic immunosuppressants (e.g. MTX, Azathioprine, cyclosporine, 6-thioguanine, mercaptopurine, mycophenolate mofetil, hydroxyurea, tacrolimus) or anakinara	4 weeks
Phototherapy	4 weeks
Systemic medications/treatments (including but not limited to oral or injectable corticosteroids, retinoids, 1,25-dihydroxy vitamin D3 and analogues, psoralens, sulfasalazine, hydroxyurea, fumaric acid derivative)	4 weeks
Topical Treatments (e.g. corticosteroids, anthralin, calcipotriene, topical vitamin D derivatives, retinoids, tazarotene, methoxsalen, trimethylpsoralens, picrolimus, tacrolimus)	2 weeks
Lithium, antimalarias, IM gold	4 weeks
Any biological therapy	6 months
Any experimental therapy or new investigational agent or participation in any other experimental/investigational trial	30 days or 5 half-life (whichever is longer)

3.4.2 Other Prohibited and/or Restricted Concomitant Medications:

- Due to potential pharmacokinetic interactions with the transporters BCRP (as inhibitor) and P-gp (as substrate), the following medications that are restricted or prohibited:
 - Breast cancer resistance protein (BRCP) substrates, such as rosuvastatin should be used with caution. If a subject is taking rosuvastatin during the study duration, the following guidelines should be used :
 - Monitor of LFTs & CPK for duration of study:
 - If 2x baseline and <3 ULN increase, consider lowering statin dose by ½
 - If > 3 ULN, stop statin for duration of study
 - If > 5 ULN, stop statin and discontinue study medication
 - If myopathy and CPK<10 ULN are observed consider lowering statin dose by ½
 - If CPK \geq 10 ULN or rhabdomyolysis, stop statin and discontinue study medication

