7.2 Study Conduct

7.2.1 Relevant Protocol Deviations

Relevant protocol deviations, which could have an impact on the primary efficacy endpoint, will be identified for all subjects who are randomized and receive study medication during the treatment period. Details of relevant protocol deviations are provided in Appendix 1.

All subjects with relevant protocol deviations will be identified prior to database lock and unblinding of treatment assignment. All relevant protocol deviations will be listed and summarized by treatment group based on All Randomized and Treated Subjects.

If there are more than 10% of the study subjects with relevant protocol deviations, a Per-Protocol analysis excluding these subjects will be performed for the primary efficacy endpoint.

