7.3.5 Prior and Concomitant Therapy

Prior medication is defined as any medication that is stopped prior to the first dose of study treatment; and concomitant medication is defined as any medication that is on-going at the time of the first dose or started after the first dose of study treatment. Medications will be coded using the WHO DRUG Dictionary Coding Guidelines (WHODrug Enhanced).

The following summary tables will be provided by treatment group:

- Concomitant Medication Summary: total subjects using medication, subjects by anatomic class/therapeutic class/generic name.
- Prior Medication Summary: total subjects using medication, subjects by anatomic class/therapeutic class/generic name.

The following by-subject listing will be provided:

- Prior and Concomitant Medications: start date, stop date, study day, anatomic class/therapeutic class/generic name/reported medication, total daily use, prior or concomitant.

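### SAP Appendix 1 omits breaches of exclusions 6m to 6v (prior non-response, pre-dose washouts) from the relevant deviations, so they neither remove a subject from the per-protocol set nor count towards its 10% trigger

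*SAP*

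**What the plan says.** SAP 7.2.1 sets the test for relevance: "Relevant protocol deviations, which could have an impact on the primary efficacy endpoint, will be identified for all subjects" who are randomized and treated. It refers to Appendix 1 for the list. The per-protocol set (SAP 6.3 and 7.5.6) and the 10% trigger (SAP 6.3, 7.2.1 and 7.5.6) both depend on that list.

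Appendix 1 contains:

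- five eligibility items: disease duration, BMI or weight, BSA, severity ("Subject with PASI score < 12 or sPGA < 3"), and non-plaque disease;
- three dosing items: wrong treatment, intake below 80% or above 120% of plan, and a gap of two or more consecutive weeks;
- under a line reading "Restricted and Prohibited medications (refer to Protocol Section 3.4.1"), one medication item: "Subjects receiving prohibited concomitant treatments while on study therapy". It cites Protocol Table 3.4.1-1.

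Protocol 3.4.1 introduces that table with "Prohibited and/or restricted medications taken prior to study drug administration in the study are described below", and its second column gives washout periods before randomization. Protocol 3.3.2 turns the washouts into exclusions 6n to 6v. It separately excludes, as 6m, subjects with "History of lack of response to ustekinumab, secukinumab or ixikizumab" or another agent targeting IL-12, IL-17 or IL-23.

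**The concern.** The list does not meet its own test. Protocol exclusions 6s and 6t bar treatments because they could affect psoriasis or its global assessment. Protocol 3.1 requires therapy to be stopped so that the drug's effect can be judged without background treatment. Yet a BMI just above 40 is a relevant deviation, while an IL-17 agent given a few weeks before Day 1 is not.

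Two mechanisms are at stake, and they differ. With a washout breach, earlier treatment may still be acting or wearing off at Day 1. Day 1 PASI is the baseline for PASI-75 (SAP 8.2), so both the baseline and the later course may partly reflect the earlier drug. A 6m breach is not carry-over: it admits a type of patient the protocol meant to keep out. In both cases the per-protocol analysis, meant to show whether deviations distort the PASI-75 comparison, would keep the subject. The breach would also not help to trigger that analysis.

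**Working it through.** **1. The plan's own figures.** Exact enumeration of the one-sided Fisher test at 0.05 with 42 per arm gives:

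- 82.6% power in the least favourable 30-point case, 35% vs 65% (stated: at least 82%);
- 99.97% power for 10% vs 60% (stated: at least 99%).

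The half-width is 1.96 × sqrt(0.25/42) = 15.1%, as stated. The chance of seeing at least one adverse event, 1 − (1 − p)^42, is 34.4%, 88.4% and 98.8% for p = 1%, 5% and 10%, which matches. So 42 per arm is a sound basis for the count in step 4.

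**2. Does the medication item reach a drug stopped before Day 1?** SAP 7.3.5 supplies both definitions:

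- for drugs in use from Day 1 on: "concomitant medication is defined as any medication that is on-going at the time of the first dose or started after the first dose";
- for drugs no longer in use by then: "Prior medication is defined as any medication that is stopped prior to the first dose of study treatment".

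A drug still ongoing at first dose is concomitant and can be caught. A drug stopped inside its washout is prior, so it fails both parts of the item: it is not concomitant, and it was not received during study therapy.

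**3. Exclusions against Appendix 1.**

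| Protocol exclusion | Window | Breach listed in Appendix 1, if drug stopped before Day 1? |
|---|---|---|
| 6m prior non-response (IL-12/17/23) | none (history) | No |
| 6n IL-12/17/23 agents | 6 months | No |
| 6o TNF inhibitors | 2 months | No |
| 6p B- or T-cell agents and similar | 3 months | No |
| 6q rituximab | 6 months | No |
| 6r systemic immunosuppressants | 4 weeks | No |
| 6s phototherapy, other systemic treatment | 4 weeks | No |
| 6t topicals | 2 weeks | No |
| 6u lithium, antimalarials, IM gold | 4 weeks | No |
| 6v experimental therapy | 6 months; or 30 days or 5 half-lives | No |

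**4. The trigger.** There are six arms in equal ratio (SAP 2.2) with 42 per arm (SAP 5), so N = 6 × 42 = 252 if all planned subjects are treated. Then 0.10 × 252 = 25.2. SAP 6.3 and 7.2.1 require more than 10%, and SAP 7.5.6 at least 10%. Both mean 26 subjects. With 25 listed deviations, 25/252 = 9.9% and the trigger is not met, however many unlisted breaches exist.

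The documents give no breach rate, so take as an assumption u subjects whose only breach is unlisted. The omission changes the trigger only if the listed count L satisfies L ≤ 25 and L + u ≥ 26.

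| u (assumed) | Total if L = 25 | Share of 252 | Values of L where the omission matters |
|---|---|---|---|
| 2 | 27 | 10.7% | 24 to 25 |
| 5 | 30 | 11.9% | 21 to 25 |
| 10 | 35 | 13.9% | 16 to 25 |

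Outside those ranges the trigger gives the same answer either way. The subjects' retention in the per-protocol set does not depend on these counts.

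**The case against.** **Intent.** The medication line points to Protocol 3.4.1, which is a washout table, so the authors may have meant to include washout breaches and worded the item loosely. That is possible. But the operative words are limited to on-study use, the SAP's own definitions exclude a stopped drug, and this reading cannot reach 6m. If inclusion was meant, the text still needs changing.

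**Partial safeguards.** Carry-over strong enough to push PASI below 12 or sPGA below 3 is caught by a listed item. Previous biologic use is a stratification factor (SAP 2.2), a covariate (SAP 7.5.1) and a Cochran-Mantel-Haenszel factor (SAP 7.5.4). Prior medications are tabulated by arm (SAP 7.3.5). These help, but none records how recently the drug was taken or removes the subject from the per-protocol set.

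**Rarity.** Protocol 3.3 allows no exceptions to entry criteria, so breaches should be few. That limits the size of the problem; it does not justify the list.

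**Size of distortion.** A reader might try to quantify the dilution. If a share s of each arm breached and responded alike in every arm, a 50-point difference (60% vs 10%) would become (1 − s) × 50, or 47.5 points at s = 5%. The documents support neither that rate nor the assumption of identical response, since breachers on active drug still receive 12 weeks of it. Even then, the 2.5-point shift is small beside a 95% half-width of 1.96 × sqrt(0.24/42 + 0.09/42) = 17.4 points, and it lies towards no effect. It is not evidence of impact.

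**Marginal breaches.** Adding all of 6n to 6v would make a late topical a relevant deviation. That is consistent, because 6t is itself framed around treatments that could affect psoriasis evaluation.

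**Conclusion.** The omission holds on the text. Breaches of exclusions 6m to 6v are not relevant deviations under Appendix 1, although several plainly meet the criterion in SAP 7.2.1 and the medication item cites a pre-dose washout table. Unless they also have a listed deviation, the subjects concerned stay in the per-protocol set and count zero towards its trigger of 26 in 252. That count assumes all planned subjects are treated.

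Two stronger conclusions are tempting and should not be drawn:

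- **That the primary result is affected.** One sentence in SAP 6.3 could be read as moving the primary analysis to the per-protocol set above 10%. But SAP 6.3 defines the efficacy population as All Randomized and Treated Subjects, SAP 7.5 applies it by default, and SAP 7.2.1 and 7.5.6 describe the per-protocol analysis as a separate one.
- **That the per-protocol analysis is barred below the trigger.** It is merely not required. SAP 7.5.6 says only that it may be performed, and SAP 9 allows further analyses on request.

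The effect is therefore confined to a conditional supportive analysis. Its size is unknown. The correction is worth making because it is cheap and must be settled while the data are blinded.

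**What to change.** Before database lock and unblinding (SAP 7.2.1 already sets that deadline for identifying deviations), add two eligibility items to Appendix 1:

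- (a) received a treatment barred by Protocol exclusions 6n to 6v within the window stated in that exclusion;
- (b) met Protocol exclusion 6m.

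Keep on-study use of prohibited treatments as a separate item.

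Cite the exclusion criteria, not Table 3.4.1-1, for the windows. The table gives TNF inhibitors 2 months in one row and any biological therapy 6 months in another, while exclusion 6o gives 2 months. The table also counts back from randomization, whereas the exclusions generally count from first administration. The sponsor should reconcile these passages; this point takes no view on which window is right. The trigger wording (will above 10% in SAP 7.2.1, may at 10% or more in SAP 7.5.6) can be aligned in the same revision.

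Protocol 3.4.1 requires CRF recording only of medications taken in the 4 weeks before dosing. Breaches of the longer windows, and of 6m, should therefore be identified from eligibility and medical-history records, and the SAP should say so.

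The cost is a few lines of SAP text, some extra blinded deviation review, and a slightly smaller per-protocol set.
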